6.1.2. Safety Population

The Safety population consists of all enrolled subjects who were exposed to at least 1 dose of study medication.

- For Stage 1, this includes all Cohort 1 subjects who were administered at least one IV infusion of ATB200 as a single agent during Stage 1.
- For Stage 2, this includes all Cohort 1 subjects who entered Stage 2 and received at least one IV infusion of 20 mg/kg ATB200 co-administered with either 130 mg or 260 mg of AT2221.
- For Stages 3 and 4, this includes all Cohort 1 subjects who entered Stage 2 Period 5 and received at least one dose of the fixed therapy 20 mg/kg ATB200 + 260 mg AT2221, as well as all the subjects who were later enrolled into Cohorts 2, 3, and 4 in Stage 3 and received at least one dose of the study medication.

Safety analyses for Stages 1 and 2 were completed and reported in iCSR-1, and they will not be repeated in this SAP unless there has been a change in the underlying data. The plan is to copy the pertinent summaries from the iCSR-1 into the final CSR. This SAP describes the analysis of safety data covered in the last bulleted item, following the co-administration of the fixed therapy 20 mg/kg ATB200 + 260 mg AT2221. All safety analyses will be conducted on the Safety population, unless otherwise specified.

6.1.3. Efficacy Population

The Efficacy population consists of all enrolled subjects who took at least 1 dose of the study medication (20 mg/kg ATB200 + 260 mg AT2221 co-administration) in Stage 3 and had both a baseline and at least 1 post-baseline assessment for any efficacy endpoint as listed in Section 4.4

(including assessments on motor function tests, muscle strength tests, PFTs, PROs, and Global Impression of Change). That is:

- For Cohort 1, this includes all subjects who entered Stage 2 Period 5 and received at least 1 dose of the 20 mg/kg ATB200 + 260 mg AT2221 co-administration and had both a baseline and at least 1 post-baseline assessment for any efficacy endpoint.
- For Cohorts 2, 3, and 4, this includes all subjects who received at least 1 dose of the 20 mg/kg ATB200 + 260 mg AT2221 co-administration and had both a baseline and at least 1 post-baseline assessment for any efficacy endpoint.

All efficacy analyses will be based on this population, unless otherwise specified.

6.1.4. PK Population

The PK population includes all subjects who were exposed to at least 1 dose of study drug and completed at least 1 PK period. Detailed description of the PK population for noncompartmental analyses is provided in Section 12.4.4.1 of Protocol ATB200-02 and in a separate Modeling and Simulation Plan for the population PK analysis which will be referenced in the final CSR.

6.2. General Methodology and Presentation

6.2.1. General Methodology

There will be no inferential statistics as no hypothesis tests were planned for this study. In general, continuous variables will be summarized using descriptive statistics including the number of subjects (n), mean, standard deviation (SD), median, the first quartile (Q1), third quartile (Q3), minimum, and maximum. Unless otherwise stated, these summaries will be provided for the raw values, absolute change from baseline, and the percent change from baseline values. Where appropriate, a 95% confidence interval (CI) for the mean change from baseline will be provided for summary purposes. Categorical variables will be summarized using frequencies (counts) and percentages.

6.2.2. General Presentation of Data

6.2.2.1. Presentation of Baseline and Background Data

Demographics, baseline characteristics, medical and surgical history, and other background information such as falls history, prior medications, prior pre-infusion medications, and history of IARs will be presented by cohort (including the total). The displayed columns will include:

- Cohort 1, Cohort 2, Cohort 3, and Cohort 4
- Total (where Total = Cohort 1 + Cohort 2 + Cohort 3 + Cohort 4)

There will be no separate presentation of baseline and background data for the different stages of the study.

6.2.2.2. Presentation of Protocol Deviations and Concomitant Pre-infusion Medications

The presentation of protocol deviations and concomitant pre-infusion medications will be similar to that of baseline and background data in Section [6.2.2.1](#).

6.2.2.3. Presentation of Post-baseline Safety Data

The results of post-baseline safety analyses, including by-visit results and changes from baseline, pre-defined limits of change (PDLC) as well as concomitant medications, non-drug therapies, study drug exposure, treatment compliance, TEAEs, and TESAEs will be presented by study stage, as follows:

- Stage 1 analyses and results are presented by SAD treatment dose.
- Stage 2 analyses and results are presented by MAD treatment dose.
- Stages 3 and 4 analyses and results (starting from Stage 2 Period 5) are presented by cohort. The columns displayed will be:
 - Cohort 1, Cohort 2, Cohort 3, Cohort 4
 - Pooled ambulatory subjects (Cohort 1 + Cohort 3 + Cohort 4)
 - Total (where Total = Cohort 1 + Cohort 2 + Cohort 3 + Cohort 4)

Note: Safety analyses for Stages 1 and 2 were reported in iCSR-1 and they will not be repeated in this SAP unless there is a change in the underlying data from Stages 1 and 2. The plan is to copy the pertinent summaries from the iCSR-1 into the final CSR.

6.2.2.4. Presentation of Post-baseline Efficacy Data

Post-baseline efficacy assessments were only collected from Stage 2 Period 5 through Stages 3 and 4. Summary results, including by-visit raw values and change from baseline values, will be presented by cohort, and the columns displayed will be:

- Cohort 1, Cohort 3, Cohort 4
- Pooled ERT-experienced ambulatory subjects (Cohort 1 + Cohort 4)
- All ambulatory subjects (Cohort 1 + Cohort 3 + Cohort 4)

Note: Efficacy results for Cohort 2 (non-ambulatory subjects) will be presented separately.

6.2.2.5. Presentation of Post-baseline Pharmacodynamic Data

Analyses results for pharmacodynamic data during Stages 1 and 2 will be copied from iCSR-1 unless it is determined that the underlying data from Stages 1 and 2 have changed.

For Stages 3 and 4 (starting from Stage 2 Period 5), analyses results will be presented similarly to the presentation of efficacy data in Section [6.2.2.4](#).

6.3. Data Management

Data management tools and methods used in this study are in accordance with applicable Amicus standards and data cleaning procedures as defined in the Data Management Plan for this study. Clinical data were collected using an electronic case report form (eCRF). The eCRF data were entered into an electronic data capture (EDC) system that is managed by a clinical research organization (CRO). Additional protocol specified data, such as laboratory and ECG data that were collected through third party vendors were integrated with eCRF data by the CRO to create complete datasets. Datasets will be created according to Clinical Data Interchange Standards

Consortium (CDISC) standards. The most current or latest version of the Study Data Tabulation Model (SDTM, version 3.2) datasets will be used. The SDTMs, Analysis Data Model (ADaM, version 2.1) datasets, all statistical and data analyses, and summary tables will be created using SAS® software version 9.4 or later. The data specifications and reviewer's guide will also be created.

6.4. Derived and Transformed Data

6.4.1. Baseline Definition

In general, baseline assessment is defined as the last non-missing result on or prior to the administration of the first dose of study medication. Baseline definitions for different variables during specific stages of the study are provided in [Table 3](#).

Table 3: Baseline Visit by Study Stage, Cohort, and Variable

Cohort	Assessment at Screening (V1, Days -28 to -1)	Assessment at Baseline (V2, Day 0)	Result Used as Baseline
Safety Data (including vital signs, laboratory data, ECG, PEs, etc) During Stages 1 and 2			
Cohort 1	X	X	Baseline is the last result obtained on/prior to V2; If result from V2 is unavailable, then use V1.
Note: Safety results for Stages 1 and 2 were reported in iCSR-1 and will not be repeated here.			
Safety Data During Stage 2 Period 5 and Stages 3 and 4			
Cohort 1	X	X	Baseline is the last result obtained on/prior to the start of the 20 mg/kg ATB200 + 260 mg AT2221 dose in Stage 2 Period 5. If the result from V9 is unavailable, then use V8. See Section 6.4.5 .
Cohorts 2, 3, and 4	X	X	Baseline is the last result obtained on/prior to V2. If result from V2 is unavailable, then use V1.
Efficacy Data, Biomarkers, and PROs During Stage 2 Period 5 and Stages 3 and 4			
Cohorts 1, 2, 3, and 4	NA	X	Baseline will be the result obtained at V2.

Abbreviations: ECG = electrocardiogram; NA = not applicable; PEs = physical examinations (which includes brief physical examination and comprehensive physical examination); PROs = patient-reported outcomes; V = visit

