Clinical Safety Laboratory Assessments, Immunological Assessments, and Urine Collections														
Serum chemistry	X		X	X	X	X	X	X	X	X	X	X	X	X
Hematology	X		X	X	X	X	X	X	X	X	X	X	X	X
Urinalysis	X		X	X	X	X	X	X	X	X	X	X	X	X
Blood sample for anti-rhGAA antibodies ^f	X		X			X	X	X	X	X	X	X	X	X

Table 11: Schedule of Assessments for Stages 3 and 4, Cohort 2 Subjects (Continued)

Assessments or Procedures ^a	Stage 3 Cohort 2 Subjects ^b													Stage 4
	Screening Days -28 to -1	Baseline Day 0 (± 1 d)	Day 1 (± 3 d)	Week 2 (± 3 d)	Week 4 (± 3 d)	Month 3 (± 3 d)	Month 6 (± 3 d)	Month 9 (± 3 d)	Month 12 (± 3 d)	Month 15 (± 3 d)	Month 18 (± 3 d)	Month 21 (± 3 d)	Month 24/ET (± 3 d)	
Blood sample for assessments of neutralizing antibodies ^f	X		X			X	X	X	X	X	X	X	X	X
Blood sample for measurement of pro-inflammatory cytokines and/or other biomarkers of immune system activation ^g	X		X			X	X	X	X	X	X	X	X	
Blood sample for exploratory biomarkers of Pompe disease and immunogenicity ^f	X		X			X	X	X	X	X	X	X	X	X
IgE measurement ^h	X	If needed												
Confirm Pompe diagnosis: blood sample for GAA genotyping if needed	X													
Miscellaneous Tests														
Collect aliquot of infusion solution			X	X	X									
Urine pregnancy ⁱ	X		X	X	X	X	X	X	X	X	X	X	X	X

Table 11: Schedule of Assessments for Stages 3 and 4, Cohort 2 Subjects (Continued)

Assessments or Procedures ^a	Stage 3 Cohort 2 Subjects ^b													Stage 4
	Screening Days -28 to -1	Baseline Day 0 (± 1 d)	Day 1 (± 3 d)	Week 2 (± 3 d)	Week 4 (± 3 d)	Month 3 (± 3 d)	Month 6 (± 3 d)	Month 9 (± 3 d)	Month 12 (± 3 d)	Month 15 (± 3 d)	Month 18 (± 3 d)	Month 21 (± 3 d)	Month 24/ET (± 3 d)	
Urine sample for Hex4	X		X	X	X	X	X	X	X	X	X	X	X	X
Pulmonary Function Tests^j														
SNIP		X				X	X	X	X	X	X	X	X	X
MIP		X				X	X	X	X	X	X	X	X	X
MEP		X				X	X	X	X	X	X	X	X	X
FVC		X				X	X	X	X	X	X	X	X	X
Muscle Strength Tests^k														
Manual muscle strength by MRC		X				X	X	X	X	X	X	X	X	X
Quantitative muscle strength by hand-held dynamometer		X				X	X	X	X	X	X	X	X	X

Table 11: Schedule of Assessments for Stages 3 and 4, Cohort 2 Subjects (Continued)

Assessments or Procedures ^a	Stage 3 Cohort 2 Subjects ^b													Stage 4	
	Screening Days -28 to -1	Baseline Day 0 (±1 d)	Day 1 (±3 d)	Week 2 (±3 d)	Week 4 (±3 d)	Month 3 (±3 d)	Month 6 (±3 d)	Month 9 (±3 d)	Month 12 (±3 d)	Month 15 (±3 d)	Month 18 (±3 d)	Month 21 (±3 d)	Month 24/ET (±3 d)		
Study Dosing															

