10.2.11. Clinical Safety Laboratory Tests

The collection, processing, and shipment of clinical laboratory samples will be fully described in the study laboratory flowchart. The parameters measured in the serum chemistry, hematology, and urinalysis are summarized in [Table 16](#), [Table 17](#), and [Table 18](#), respectively. Blood and urine samples for clinical laboratory evaluations will be taken before study treatment administration in Stages 1, 2, 3, and 4 and will be collected according to the Schedule of Assessments tables.

The investigator (or his/her designee) will review each laboratory report from the central laboratory and assess any out of range laboratory results as “not clinically significant” or “clinically significant”. Any results which are considered CS should be confirmed in a repeat test at the investigator’s discretion. The investigator should consider repeat testing of persistent CS results until the analyte returns to normal, or until an etiology is determined. The investigator (or his/her designee) will sign and date all laboratory reports.

All CS laboratory results will be reported as an AE or SAE, as appropriate.

If any results demonstrate, in the investigator’s opinion, a CS abnormality that the subject has not previously experienced, then the subject should be asked to return as soon as possible for an unscheduled visit, so that repeat specimens can be obtained.

Clinically significant values are provided in [Appendix 2](#).

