6.5.2. Visit Windows for Cohorts 2, 3, and 4 Data

For Cohorts 2, 3, and 4, the visit windows in [Table 5](#) will be used for analyses of safety and PD markers, and [Table 6](#) for the efficacy data.

Table 5: Visit Windows for Analyses of Cohorts 2, 3, and 4 Safety and Pharmacodynamic Data

Visit Name	Target Day	Visit Windows
Baseline	NA	Baseline is Visit 2
Day 1	1	Day 1 is Visit 3
Week 2	15	Day 2 – 22
Week 4	29	Day 23 – 60
Month 3	91	Day 61 – 136
Month 6	181	Day 137 – 226
Month 9	271	Day 227 – 316
Month 12	361	Day 317 – 406
Month 15	451	Day 407 – 496
Month 18	541	Day 497 – 586
Month 21	631	Day 587 – 676
Month 24	721	Day 677 – 811
Month 30	901	Day 812 – 991
Month 36	1081	Day 992 – 1171
Month 42	1261	Day 1172 – 1351
Month 48	1441	Day 1352 – 1531
Month 54	1621	Day 1532 – 1711
Month 60	1801	Day 1712 – 1891
Month X ^a	T _{MONTH X}	d1 – d2

Abbreviation: NA = not applicable

^a Target day of planned assessment visit at Month X is denoted T_{MONTH X} and it is given by T_{MONTH X} = (30 * X + 1). For example, the target day at Month 54 = T_{MONTH 54} = 30 * 54 + 1 = 1621. Target day of assessment visit immediately before Month X is given by T_{BEFORE}. For example, T_{BEFORE} = T₄₈ = (30 * 48 + 1) = 1441. Target day of assessment visit immediately after Month X is given by T_{AFTER}. For example, T_{AFTER} = T₆₀ = (30 * 60 + 1) = 1801. The visit windows are then given as d1 – d2, where d1 = ([T_{BEFORE} + T_{MONTH X}] / 2) + 1 and d2 = (T_{MONTH X} + T_{AFTER}) / 2.

Table 6: Visit Windows for Analyses of Cohorts 2, 3, and 4 Efficacy Data

Visit Name	Target Day	Visit Windows
Baseline	NA	NA (Baseline is Visit 2)
Month 3	91	Day 61 – 136
Month 6	181	Day 137 – 226
Month 9	271	Day 227 – 316
Month 12	361	Day 317 – 406
Month 15	451	Day 407 – 496
Month 18	541	Day 497 – 586
Month 21	631	Day 587 – 676
Month 24	721	Day 677 – 811
Month 30	901	Day 812 – 991
Month 36	1081	Day 992 – 1171
Month 42	1261	Day 11872 – 1351
Month 48	1441	Day 1352 – 1531
Month 54	1621	Day 1532 – 1711
Month 60	1801	Day 1712 – 1891
Month X ^a	T _{MONTH X}	d1 – d2
LAV	Target day corresponding to the LAV	Visit window corresponding to the LAV

Abbreviations: LAV = last assessed value; NA = not applicable

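### For Cohorts 2 to 4, SAP Table 3 sets the safety-laboratory baseline to Screening and passes over the pre-dose Day 1 sample, to which Table 5 gives a visit row of its own

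*SAP*

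**What the plan says.** SAP 6.4.1 opens with a general rule: "baseline assessment is defined as the last non-missing result on or prior to the administration of the first dose of study medication". It then refers to Table 3 for specific stages and variables. The heading of Table 3's first safety block lists laboratory data among the variables meant. In the block for Stage 2 Period 5 and Stages 3 and 4, the Cohorts 2, 3 and 4 row reads, apart from one punctuation mark, like the Cohort 1 row for Stages 1 and 2: "Baseline is the last result obtained on/prior to V2; If result from V2 is unavailable, then use V1". For Cohort 1 in the later stages, the baseline is the last result up to the start of the combination dose at Visit 9: "If the result from V9 is unavailable, then use V8".

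Protocol Tables 11, 12 and 13 mark serum chemistry, hematology and urinalysis at Screening and on Day 1 and leave the Baseline column empty. Protocol 10.2.11 fixes the timing: "Blood and urine samples for clinical laboratory evaluations will be taken before study treatment administration in Stages 1, 2, 3, and 4".

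SAP 6.5.2 says of the Table 5 windows that they "will be used for analyses of safety and PD markers". Table 5 has one row where "Baseline is Visit 2" and a separate row where "Day 1 is Visit 3". SAP section 10 bases the by-visit safety summaries on these windows, and SAP 10.4 summarises actual values, changes and percent changes for laboratory parameters.

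**The concern.** In Table 3 the use of Screening looks like a fallback for a missed Visit 2 sample. Because no laboratory sample is scheduled at Visit 2, it is in practice the rule for every subject. A later value, drawn on the dosing day before the infusion, is passed over.

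Two things follow. First, a Day 1 laboratory row of change from baseline compares two pre-treatment samples, and a reader of the table could take it for an early effect of treatment. Second, every later laboratory change is measured from the older value, as are the limits of change defined relative to baseline. With 4 to 8 planned subjects per cohort, ordinary variation in one subject can move a cohort mean.

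**Working it through.** **1. Table 5 reproduced.** The footnote gives target T = 30X + 1, lower limit (T_before + T)/2 + 1 and upper limit (T + T_after)/2. For Month 24, T = 721, with neighbours 631 and 901. The limits are (631 + 721)/2 + 1 = 677 and (721 + 901)/2 = 811, as stated. Extending the formula to the week rows, 15 of the 16 numeric windows agree. The exception is Week 2: the formula gives (1 + 15)/2 + 1 = Day 9 as the start, and Table 5 states Day 2. This is because Day 1 is kept as a one-day row for Visit 3 alone. For scheduled laboratory samples, that row therefore holds the pre-dose Day 1 sample.

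**2. The two baseline rules applied to the schedule.**

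| Visit | Scheduled laboratory sample | Eligible under Table 3 (to V2, else V1) | Eligible under the general 6.4.1 rule |
|---|---|---|---|
| V1 Screening, Days -28 to -1 | yes | yes, selected | yes, but not the last |
| V2 Baseline, Day 0 | no | nothing to select | nothing to select |
| V3 Day 1, pre-dose | yes | no, later than V2 | yes, selected |

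Table 3 selects V1 and the general rule selects V3.

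**3. Age of the baseline.** Protocol 10.1.1 places Screening no more than 28 days before the start of study treatment. The lag is thus up to 28 days under Table 3 and 0 days under the general rule.

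**4. The Day 1 change.** Under Table 3 it is V3 pre-dose minus V1. As an illustration, assume a stable analyte with independent occasions and within-subject SD σ. The Day 1 change then has mean 0 and SD √(σ² + σ²) = 1.41σ, which is noise only. Under the general rule V3 is the baseline itself, the Day 1 change is 0, and Week 2 is the first post-dose laboratory row.

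**5. Reach.**
- Planned subjects in Cohorts 2 to 4: (4 to 6) + 5 + (6 to 8) = 15 to 19.
- Table 8 limits that refer to baseline: albumin, the composite bilirubin limit, calcium, phosphorus, potassium, sodium, the composite uric acid limits, hemoglobin change and the composite platelet limits. CK also has a part relative to baseline, but the SAP does not say whether that uses the safety or the pharmacodynamic baseline.
- Table 8 limits that do not use baseline: ALT, AST and their combinations with bilirubin, bicarbonate, eosinophils, and the absolute limits for bilirubin, uric acid, hemoglobin and platelets.

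**The case against.** The best defence is that Table 3 is a deliberate specific rule. The general sentence in 6.4.1 is qualified as general and hands over to the table, and Protocol 10.1.2 permits the Screening value when an assessment was not done at Baseline. This stands in part: using Screening breaches no protocol requirement. But the permission does not call for discarding a later pre-dose sample. The SAP gives no reason for doing so, and its list of changes from the protocol (section 11) does not mention baseline.

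It is also fair that the Day 1 row in Table 5 is needed for vital signs, ECG and physical examination, which are scheduled at both Baseline and Day 1. The SAP never calls Day 1 post-baseline. That a laboratory change is tabulated there follows from the separate row together with the change-from-baseline summaries in 10.4.

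Some stronger readings are tempting but not supported:
- **Screening is contaminated by prior ERT and Day 1 is not.** Cohorts 2 and 4 enter on alglucosidase alfa, which Protocol 8.7 prohibits only once ATB200 has begun. No washout is specified, so both samples precede the switch.
- **The lag is 31 days, adding the visit window.** Protocol 10.1.1 counts the 28 days to the start of treatment.
- **Cohort 1 follows the opposite principle.** At study entry it has the same V2-else-V1 rule. Visit 9 is a re-baseline after earlier ATB200 doses and would differ in kind from any entry baseline. The pooled and Total columns in SAP 6.2.2.3 do mix the rules.
- **The Day 1 sample inflates the limit-of-change counts.** SAP 10.4 restricts these to values collected after first dose.

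**Conclusion.** The inconsistency is real and should be corrected. For all scheduled laboratory samples in Cohorts 2 to 4 (15 to 19 planned subjects), Table 3 yields a Screening baseline up to 28 days before first dose, against the SAP's own general definition, and the layout of Table 5 turns a pre-dose sample into a change row. The older baseline carries into all later laboratory changes and the baseline-relative Table 8 limits. The CK and Hex4 pharmacodynamic analysis has its own baseline rule in SAP 10.5 and is not part of this point.

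The consequence is moderate. The study is descriptive with no hypothesis tests, most percentage limits also require a value outside the normal range, and the documents give no data on how far Screening and Day 1 values differ. The size and direction of any shift are therefore unknown. The conclusion assumes samples were taken as scheduled; an unscheduled result between Screening and Visit 2 would become the baseline under Table 3. A reader might infer that the whole safety baseline is faulty. It is not: vital signs, ECG and physical examination are scheduled at Visit 2.

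**What to change.** Add one line to SAP Table 3 for safety laboratory data in Cohorts 2, 3 and 4: baseline is the last non-missing result before the first dose, that is, the Visit 3 pre-dose sample or, if missing, the latest earlier result. In the by-visit laboratory tables, remove the Day 1 change row for these cohorts or label it as pre-dose baseline. Leave the Visit 2 baseline for vital signs, ECG and physical examination unchanged, and keep the Day 1 row in Table 5 for those assessments.

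The cost is one table line, one change to the laboratory baseline flag and a footnote explaining any differences from earlier interim outputs. SAP section 2 has the plan finalised before database lock, so the change belongs there.

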6.4.2. Multiple Baseline Assessments

For continuous variables, if multiple baseline measurements were taken at the same visit, the last result prior to the first dose of study medication will be used. If it is not possible to determine the last result, then the average will be used as the baseline value for analysis purposes.

6.4.3. Change from Baseline and Percent Change from Baseline

Analysis of change from baseline will include only subjects who have assessment at both baseline and the post-baseline time point being analyzed. That is:

- Change from baseline is calculated as: Change = post-baseline result – baseline result.
- Percent change from baseline is calculated as: $100 * (\text{Change from baseline} / \text{Baseline result})$.

If either the baseline or the post-baseline result is missing, the change from baseline and the percentage change from baseline are set to missing.

